8.1.5 Derivation of EAER

The exposure adjusted event rate (EAER) will be the number of AEs including repeat occurrences in individual subjects divided by the total time at risk scaled to 100 subject-years and calculated using:

$$EAER = 100N_{AE} / \sum_{i=1}^N T_{Risk,i} \quad (13)$$

where N_{AE} is the total number of AEs.

No confidence interval will be computed for EAER.

8.1.6 Analysis of the primary safety variable

All TEAEs will be summarized descriptively by PS0011 treatment group, primary SOC, HLT, and PT. This summary will include the number and percentage of subjects experiencing the event, the number of events, EAIR with associated 95% confidence interval based upon the Chi-Square distribution (Ulm, 1990), and the EAER.

8.2 Other safety analysis

8.2.1 TEAEs

The following summaries will be provided by PS0011 treatment group and for the “All bimekizumab” group. In addition, all summaries of TEAEs “per 100 subject years” will display EAIR and EAER:

- Incidence of TEAEs – Overview
- Incidence of TEAEs per 100 subject years by SOC, HLT and PT
- Incidence of TEAEs per 100 subject years by SOC, HLT, PT and by Timing of Onset Relative to Anti-bimekizumab Antibody Status
- Incidence of TEAEs by Decreasing Frequency of PT
- Incidence of TEAEs by Maximum Severity, SOC, HLT and PT
- Incidence of Non-Serious TEAEs by SOC, HLT and PT
- Incidence of Non-Serious TEAEs Above Reporting Threshold of 5% by SOC and PT

The incidence of TEAEs per 100 subject years will also be summarized for PS0010 and PS0011 combined, where treatment emergence and exposure at risk are relative to the first dose of study drug in PS0010. In the case of a subject that switches study treatment when starting PS0011, exposure at risk to PS0010 treatment will end the day prior to the first PS0011 dose. Adverse events that occur on the PS0011 baseline visit date will be attributed to the PS0010 treatment.

The only exception to this definition is for the following types of events:

- Those that code to a High Level Term (HLT) of “Injection Site Reactions”
- Those which have been designated as an Injection Reaction on the AE CRF and do not code to a System Organ Class (SOC) of “Investigations”
- Those which have been identified as a hypersensitivity reaction or an anaphylactic reaction

When any of these events occur on the date of treatment switch at PS0011 Baseline, the AE will be attributed to the treatment initiated in PS0011.

All AE summaries will be ordered alphabetically by SOC and HLT within SOC and in terms of decreasing frequency for PT within HLT in the “All bimekizumab” treatment group.

For each subject and each AE, the worst severity recorded will be attributed and used in the by-severity summaries. Similarly, the worst causality (most related to treatment) will be attributed and used in the by-causality summaries. If severity or causality is missing, the worst case will be assumed.

If the intensity of an AE is unknown, it will be considered as severe. If the relationship to study drug is missing, it will be considered as related.

Additional tables will summarize TEAEs by relationship to study medication, TEAEs leading to withdrawal from the study, treatment-emergent SAEs, and deaths:

- Incidence of TEAEs by Relationship, SOC, HLT and PT
- Incidence of Non-Serious TEAEs by Relationship, SOC, HLT and PT
- Incidence of Non-Serious TEAEs Above Reporting Threshold of 5% by Relationship, SOC and PT
- Incidence of Serious TEAEs per 100 subject years by SOC, HLT and PT
- Incidence of Serious TEAEs by Relationship, SOC, HLT and PT
- Incidence of TEAEs Leading to Discontinuation by SOC, HLT and PT
- Incidence of TEAEs Leading to Death by SOC, HLT and PT
- Incidence of TEAEs Leading to Death by Relationship, SOC, HLT and PT

The incidence of serious TEAEs per 100 subject years will also be summarized for PS0010 and PS0011 combined, where treatment emergence and exposure at risk are relative to the first dose of study drug in PS0010. In the case of a subject that switches study treatment when starting PS0011, exposure at risk to PS0010 treatment will end the day prior to the first PS0011 dose. Adverse events that occur on the PS0011 baseline visit date will be attributed to the PS0010 treatment. The only exception to this definition is for the following types of events:

- Those that code to a High Level Term (HLT) of “Injection Site Reactions”
- Those which have been designated as an Injection Reaction on the AE CRF and do not code to a System Organ Class (SOC) of “Investigations”
- Those which have been identified as a hypersensitivity reaction or an anaphylactic reaction

When any of these events occur on the date of treatment switch at PS0011 Baseline, the AE will be attributed to the treatment initiated in PS0011.

The following by-subject listings will be provided:

- All serious TEAEs
- All TEAEs leading to discontinuation of study treatment

- All death data
- All TEAEs and all non-TEAEs
- All treatment-emergent adverse drug reactions
- All AEs of special monitoring (AESM).

The following are AESM that require special statistical analyses:

1. Serious infections, opportunistic infections including TB and fungal infections

Serious infections will be identified based on MedDRA classification (SOC “Infections and infestations”) using the “Any SAE” table. A separate table does not need to be produced to summarize these events.

Fungal infections will be summarized in a stand-alone table which presents EAIR and EAER. The table will include all TEAEs which code into the high level group term (HLGT) of “Fungal infectious disorders”.

The number and percentage of subjects experiencing fungal infections will be summarized by region and country by PS0011 treatment group. This summary will also include the number and percentage of subjects experiencing the PT “Oral Candidiasis.” by region and country.

Opportunistic infections (including tuberculosis) will be summarized in a stand-alone table which presents EAIR and EAER. The table will include all TEAEs identified using UCB-defined search criteria as described in [Section 12.2](#).

2. Malignancies, including lymphomas

These events will be presented in two stand-alone tables which include EAIR and EAER:

- One table will be based on the criteria standard MedDRA query (SMQ) = “Malignant or unspecified tumours (SMQ)”
- One table will be based on the criteria SMQ = “Malignant tumours (SMQ)”.

Note that the events included in the “Malignant tumours” table will be a subset of the events included in the “Malignant or unspecified tumours” table. The SMQ search should include all TEAEs which code to a PT included in the Scope = Narrow group within each SMQ.

The output tables will include two different overall incidence rows. The first overall incidence row will summarize “Any malignancies (including unspecified)” or “Any malignancies” (depending on the table) and this row will summarize the incidence of all AEs flagged for inclusion in the table, regardless of the HLT it codes to. The second overall incidence row will summarize “Any malignancy (including unspecified, excluding non-melanomic skin cancers)” or “Any malignancy (excluding non-melanomic skin cancers)” (depending on the table) and this row will summarize the incidence of AEs flagged for inclusion in the table, excluding those which code to an HLT of “skin neoplasms malignant and unspecified (excl melanoma)”

3. Major cardiovascular events

Major cardiovascular events will be presented in a stand-alone table which includes EAIR and EAER. The table will include TEAEs that are identified using the following UCB-defined search criteria:

- All serious TEAEs which code to a PT included in the Scope = Broad and/or Scope = Narrow groups of the following SMQs:
 - Haemorrhagic central nervous system vascular conditions (SMQ)
 - Ischaemic central nervous system vascular conditions (SMQ).
 - All serious TEAEs which code to a PT included in the HLT “Ischaemic coronary artery disorders” except events coding to a PT “Chest pain” or “Chest discomfort”
 - All serious TEAEs which code to a PT included in any of the following HLTs: Heart Failures NEC, Left Ventricular Failures, or Right Ventricular Failures and which also code to the SOC of Cardiac Disorders as Primary SOC.

4. Cytopenias

These events will be presented in a stand-alone table that is based on the SMQ = “Haematopoietic cytopenias”. The SMQ search should include all serious TEAEs which code to a PT included in the Scope = Broad and/or Scope = Narrow groups within the SMQ.

5. Neuropsychiatric events (in particular depression and suicide)

These events will be presented in a stand-alone table including EAIR and EAER. The table will be based on the SMQ = “Depression and suicide/self-injury (SMQ)”. The SMQ search will include all TEAEs which code to a PT included in the Scope = Broad and/or Scope = Narrow groups within the SMQ.

6. Inflammatory bowel disease

These events will be presented in a stand-alone table which includes EAIR and EAER. The table will include all TEAEs which code into the HLT of “Colitis (excl infective)”.

7. Anaphylactic reaction

Anaphylactic reactions will be summarized together in a stand-alone table.

The first row within the body of the table will be labeled “Any hypersensitivity reaction/anaphylactic reaction” and will represent the overall incidence of subjects who reported at least one hypersensitivity reaction or at least one anaphylactic reaction.

The second row within the body of the table will be labeled “Any hypersensitivity reaction” and will represent the overall incidence of subjects who reported at least one hypersensitivity reaction.

The third row within the body of the table will be labeled “Any anaphylactic reaction” and will represent the overall incidence of subjects who reported at least one anaphylactic reaction.

Following these three overall incidence rows, all TEAEs that have been identified as either a hypersensitivity reaction or an anaphylactic reaction will be summarized (together – not broken out by type) by SOC, HLT and PT.

Hypersensitivity reactions and anaphylactic reactions will be identified as follows:

a) Hypersensitivity reactions

All TEAEs that either emerged on the same day as when a study medication injection reaction was received, or that emerged one day after a study medication injection was received, which code to a PT which contains the term “hypersensitivity” will be considered to be a hypersensitivity reaction and included in the summary table as such.

b) Anaphylactic reactions

An algorithmic approach will be used to identify TEAEs that are considered to be anaphylactic reactions. PTs are separated into the four distinct categories (A, B, C, D) prior to the algorithmic approach being applied.

All TEAEs that either emerged on the same day as when a study medication injection reaction was received, or that emerged one day after a study medication injection was received, and which fulfill any of the three criteria described in [Section 12.3](#) will be included in the summary table.

8. Hepatic events and DILI

Although not officially considered to be AEs of special monitoring, hepatic events are nonetheless considered to be interesting enough to be summarized in stand-alone tables.

Hepatic events will be summarized in a stand-alone table that includes all TEAEs in the SMQ “Drug related hepatic disorders – comprehensive search (SMQ)”. Note that the following two sub-SMQs are to be excluded: “Liver neoplasms, benign (incl cysts and polyps)” and “Liver neoplasms, malignant and unspecified (SMQ)”.

The SMQ search should include all TEAEs (regardless of whether they have been judged as related to study medication or not) which code to a PT included in the Scope = Narrow group within each SMQ.

Hy’s Law cases are to be reported separately in the liver function test summary table (with adjudication for “Potential drug-induced liver injury” cases).

Additional tables will summarize TEAEs by responder status (defined as PS0010 Week 12 PASI90 response):

- Incidence of TEAEs – Overview
- Incidence of TEAEs per 100 subject years by SOC, HLT and PT
- Incidence of Serious TEAEs per 100 subject years by SOC, HLT and PT
- Incidence of Fungal Infectious Disorders per 100 subject years by SOC, HLT and PT

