6.2 Exclusion criteria

Subjects are not permitted to enroll in the study if any of the following criteria are met:

1. Subject has previously participated in this study.
2. Female subjects who plan to become pregnant during the study or within 20 weeks following last dose of study medication. Male subjects who are planning a partner pregnancy during the study or within 20 weeks following the last dose.
3. Subject has any medical or psychiatric condition that, in the opinion of the Investigator, could jeopardize or would compromise the subject's ability to participate in this study. Note: For any subject with an ongoing serious adverse event (SAE), or a history of serious infections (including herpes zoster or hospitalizations) in PS0010, the Medical Monitor must be consulted prior to the subject's entry into PS0011.
4. Subject must have a negative interferon gamma release assay (IGRA) as measured at Week 8 of PS0010.
5. Any subject who meets any withdrawal criteria in the feeder study (PS0010) is excluded from participating in the extension study (PS0011).

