14.1 Definition of analysis sets

The Enrolled Set (ES) will consist of all subjects who have given informed consent for PS0011.

The Safety Set (SS) will consist of all subjects who receive at least 1 dose of the study medication in PS0011.

The Full Analysis Set (FAS) will consist of all enrolled subjects who receive at least 1 dose of the study medication in PS0011 and have a valid efficacy measurement for PASI at Baseline of PS0011.

The Pharmacokinetics Per-Protocol Set (PK-PPS) will consist of all enrolled subjects who receive at least 1 dose of the study medication in PS0011 and provide at least 1 quantifiable plasma concentration postdose in PS0011.

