3.5.2 Safety Set

The SS will consist of all subjects who receive at least one dose of the study medication in PS0011.

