8 SAFETY ANALYSES

All safety summaries and listings will be performed using all subjects in the SS.

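### The combined PS0010+PS0011 TEAE tables count PS0010 time only for subjects who went on to PS0011, which biases incidence rates of entry-barring events downward

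*SAP*

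**What the plan says.** Population. SAP 8 opens with "All safety summaries and listings will be performed using all subjects in the SS". SAP 3.5.2 defines that set: "The SS will consist of all subjects who receive at least one dose of the study medication" in PS0011. Protocol 14.1 agrees: "The Safety Set (SS) will consist of all subjects who receive at least 1 dose of the study medication in PS0011". SAP 3.5 defines no set for the two studies together, and 8.2.1 writes no exception.

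Clock. SAP 8.2.1 plans a combined table for all TEAEs, "The incidence of TEAEs per 100 subject years will also be summarized for PS0010 and PS0011 combined", and another for serious events: "The incidence of serious TEAEs per 100 subject years will also be summarized for PS0010 and PS0011 combined". In both, treatment emergence and "exposure at risk are relative to the first dose of study drug in PS0010". If a subject changes treatment on entering PS0011, "exposure at risk to PS0010 treatment will end the day prior to the first PS0011 dose".

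Entry. Protocol 6.1, criterion 3, requires that PS0010 dosing and the study itself were finished with no withdrawal criterion met. Protocol 6.2, criterion 5, repeats this from the other side: "Any subject who meets any withdrawal criteria in the feeder study (PS0010) is excluded from participating". A note to 6.2, criterion 3, sends a subject with an ongoing SAE, or with a serious infection in PS0010, to the Medical Monitor before entry; it does not exclude that subject outright.

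**The concern.** Population and clock do not match. The clock starts when PS0010 treatment starts, but membership is decided about 12 weeks later and depends on what happened in those weeks. Anyone who died in PS0010, or had an adverse event that met a PS0010 withdrawal criterion, is outside the Safety Set. Such events cannot reach the numerator, while everyone else's PS0010 weeks fill the denominator. For those events the PS0010 weeks are immortal time.

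Long-term safety is the primary objective. A rate counted from the first PS0010 dose will naturally be read as covering everyone who started treatment. As planned, it leaves out the early events that were severe enough to stop treatment.

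**Working it through.** **Inputs**
- Expected injections for a treatment completer: 24, two per dose (SAP 7), so 12 doses.
- Tail after the last dose: 140 days (SAP 8.1.3).
- PS0010 treatment period: 12 weeks = 84 days (Protocol 2.2.1).
- Planned PS0010 randomization: 240 (Protocol 14.8).
- Assumed, because the documents do not give them: the event hazard λ, the share f of PS0010 first serious events that bar entry, and the number of PS0010 withdrawals for an adverse event.

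**1. Reproduce the plan's own duration.** The last dose falls at (12 − 1) × 4 = Week 44, or 308 days. Then 44 + 140/7 = 64 weeks, which matches the stated maximum (SAP 2.3.3).

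**2. Share of PS0010 time.** For a full completer, 84/(84 + 308 + 140) = 84/532 = 15.8%. If the last PS0011 dose is at Week 12, PS0011 risk time is 12 + 20 = 32 weeks and the share is 12/44 = 27.3%.

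**3. Direction.** A subject whose first event falls within the 84 PS0010 days contributes one event in at most 84 days, which is at least 100/(84/365.25) = 435 per 100 subject-years. Leaving that subject out lowers the EAIR unless the true EAIR already exceeds 435.

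**4. Serious-TEAE EAIR.** Let T1 and T2 be the PS0010 and PS0011 risk times, S = exp(−λT1), and m = 1/λ − T1·S/(1 − S), the mean time to an event that occurs within T1. Per subject dosed in PS0010, the Safety Set captures:
- events: (1 − f)(1 − S) + S(1 − exp(−λT2))
- time: (1 − f)(1 − S)m + S·T1 + S(1 − exp(−λT2))/λ

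For small λ, reported/true is close to 1 − f × T1/(T1 + T2), that is 1 − 0.158f with full follow-up. This treats non-entry for reasons other than the event as uninformative.

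Example with λ = 6 per 100 subject-years, f = 0.5 and full follow-up: events 0.00685 + 0.06998 = 0.07683; years 0.2276 + 1.1663 = 1.3939; EAIR 5.51; reported/true = 0.92.

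Reported/true for λ from 3 to 10 per 100 subject-years:

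| f | 12 + 64 weeks | 12 + 32 weeks | PS0010 time only |
|---|---|---|---|
| 0.25 | 0.96 | 0.93 | 0.75 |
| 0.5 | 0.92 | 0.86 | 0.50 |
| 1 | 0.83–0.84 | 0.72–0.73 | 0 |

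The last column is 1 − f. It applies to any treatment whose time at risk consists entirely of PS0010 weeks.

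**5. Add-back illustration.** Suppose the Safety Set rate is 6 per 100 subject-years and 5 of 240 were withdrawn for an adverse event, half of them with a serious one at 6 weeks and the rest followed for 6 + 20 weeks. The other 235 give 19.66 events in 327.7 years. Adding 2.5 events and 0.29 + 1.25 years gives 22.16/329.3 = 6.7, a ratio of 0.89.

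**6. All TEAEs.** With 2 to 12 of 240 withdrawn and a first-TEAE rate of 150 to 400 per 100 subject-years, the any-TEAE EAIR ratio is 0.95–0.99. For the EAER, if each withdrawn subject contributes one to three events and keeps the 140-day tail, the ratio runs from 0.95 to 1.01.

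**The case against.** The best defence is that these are two supplementary descriptive tables. The primary safety analysis (SAP 8.1.6) counts only from the first PS0011 dose, no inferential testing is planned (Protocol 14.2), and no decision rule uses the combined tables. A rate conditional on entering the extension can be interpreted if it is labelled as such. The note to Protocol 6.2, criterion 3, also suggests that f for serious events may be well below 1. The PS0010 withdrawal criteria are not in these documents; Protocol 6.3 gives only those of PS0011. All of this stands and limits both size and priority. It does not remove the mismatch, and the SAP contains no such label.

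A reader might infer more than the documents support:
- **That every combined rate is too low.** Only events that barred entry are lost. The any-TEAE EAIR hardly moves, and the EAER has no assured direction.
- **That the understatement is 27% or 36%.** Those figures are 1 − 448/(2 × 84 + 448) and 1 − 448/(3 × 84 + 448). They need every such event to block entry and an early hazard assumed to be doubled or tripled.
- **That a 480mg column is shown falsely clean.** The layout of the combined tables is not stated. SAP 8.2.1 introduces its summaries by PS0011 treatment group, and those groups contain no 480mg. The rule for time on PS0010 treatment suggests columns by treatment received, but that is an inference. Placebo PASI90 responders stay on placebo and keep adding PS0011 time, and no placebo response rate is given.
- **That nothing else combines the two studies.** Protocol 14.7 and SAP 4.3 plan combined reviews for the DMC. Those fall under a separate DMC SAP and do not change the population of the 8.2.1 tables.

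**Conclusion.** The point holds for deaths and adverse events that barred entry to PS0011: in both combined tables their incidence rates are biased downward. The population, the selection and the direction follow from the text. The size does not, because f, the hazard and the PS0010 withdrawal counts are all assumptions. Under a constant hazard the serious-TEAE EAIR is low by about 0.16 × f with full follow-up, and by more when PS0011 follow-up is shorter.

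If the tables turn out to have columns by treatment received, all time attributed to 480mg comes from entrants, since every 480mg subject switches to 320mg. The rate of entry-barring events in that column is then zero by construction. Placebo time is affected to the extent that placebo subjects switch, so comparisons between columns would be distorted as well.

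This should be fixed, but it is not critical: the PS0011-only primary table is not affected by this rule.

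**What to change.** - In SAP 3.5, define a Combined Safety Set: all subjects who received at least one dose of study medication in PS0010.
- In SAP 8.2.1, base both combined tables on it, and state the exception in SAP 8.
- For subjects who did not enter PS0011, count events and time from the first PS0010 dose to the last PS0010 dose + 140 days, or to last contact or death if earlier.
- State that, for subjects who switch, time on PS0010 treatment still ends the day before the first PS0011 dose. Risk windows then differ by entry status, and a table footnote should say so.
- State the column layout of both tables.
- If a Safety Set version is also kept, label it as conditional on entering PS0011.

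The cost is SAP wording and reprogramming of two descriptive tables. No new data are needed: SAP 4.3 already has PS0010 data feeding the combined DMC outputs. Incidence rates, above all for serious events, are likely to become somewhat less favourable.
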